### **7.1.2 Nivolumab Dosing**

Participants 18 years of age and older, or age of majority, should receive nivolumab at a dose of 480 mg as a 30-minute infusion on Day 1 of each treatment cycle until progression, unacceptable toxicity, withdrawal of consent/assent, or completion of 104 weeks of treatment, whichever occurs first.

Participants should begin study treatment within 3 calendar days of randomization

The dose of BMS-986205 (for participants in Arm A that continue receiving BMS-986205) should be given before the dose of nivolumab, but specific timing is not required. Participants should begin study treatment within 3 calendar days of randomization.

There will be no dose escalations or reductions of nivolumab allowed. For Q4W dosing cycles, participants may be dosed within a  $\pm 3$  day window. For this dosing cycle, participants may be dosed no less than 25 days and no more than 31 days between doses. In extenuating circumstances in which the participant cannot make the dosing schedule within the 3-day window, the BMS Medical Monitor/designee should be contacted.

Premedication is not recommended for the first dose of nivolumab.

Participants should be carefully monitored for infusion reactions during nivolumab administration. After the first nivolumab infusion, subjects should be monitored per local/institutional guidelines. If no such guidelines exist, an observation period of 2 hours after the end of the nivolumab infusion is suggested.

If an acute infusion reaction is noted, participants should be managed according to [Section 7.7.5](#).

Doses of nivolumab may be interrupted, delayed, or discontinued depending on how well the participant tolerates the treatment. Dosing visits are not skipped, only delayed.

Nivolumab Injection, 100 mg/10 mL (10 mg/mL) is to be administered as an IV infusion through a 0.2-micron to 1.2-micron pore size, low-protein binding in-line filter at the protocol-specified doses. It is not to be administered as an IV push or bolus injection. When the dose is based on participant's weight (ie, mg/kg), nivolumab injection can be infused undiluted (10 mg/mL) or diluted with 0.9% Sodium Chloride Injection, USP or 5% Dextrose Injection, USP to protein concentrations as low as 0.35 mg/mL. When the dose is fixed (eg, 480 mg flat dose), nivolumab injection can be infused undiluted or diluted so as not to exceed a total infusion volume of 160 mL. Nivolumab infusion must be promptly followed by a saline flush to clear the line. Instructions for dilution and infusion of nivolumab injection will be provided in the pharmacy binder. Care must be taken to assure sterility of the prepared solution as the product does not contain any antimicrobial preservative or bacteriostatic agent.

Nivolumab infusions are compatible with polyvinyl chloride (PVC) or polyolefin containers and infusion sets, and glass bottles.

Additional information on study drug preparation, handling and administration can be found in the Pharmacy Manual.

The selection and timing of dose for each participant is provided in [Table 7.1-1](#).

## 7.2 Method of Treatment Assignment

As of 19-Apr-2018, enrollment in the study has been closed.

All participants will be centrally randomized using an Interactive Response Technology (IRT). Before the study is initiated, each user will receive log-in information and directions on how to access the IRT. After the participant's initial eligibility is established and informed consent has been obtained, the participant must be enrolled into the study by calling an IRT to obtain the participant number. Every participant who signs the informed consent form must be assigned a participant number in IRT. The investigator or designee will register the participant for enrollment by following the enrollment procedures established by BMS. The following information is required for enrollment:

- Date that informed consent was obtained
- Year of birth
- Gender at birth

Once enrolled in IRT, enrolled participants who have met all eligibility criteria will be ready to be randomized through the IRT. The following information is required for participant randomization:

- Participant number
- Year of birth
- PD-L1 status (PD-L1 positive vs PD-L1 negative/indeterminate) entered by vendor ; PD-L1 expression will be determined using the Dako PD-L1 IHC 28-8 pharmDx assay.
- BRAF V600 mutational status
- M Stage at screening (see [Appendix 7](#))

Participants meeting all eligibility criteria will be randomized in a 1:1 ratio and stratified by PD-L1 status, BRAF status, and AJCC M stage as described below:

- PD-L1 status
  - PD-L1 positive ( $\geq 1\%$  tumor cell membrane staining in a minimum of 100 evaluable tumor cells) vs
  - PD-L1 negative ( $< 1\%$  tumor cell membrane staining in a minimum of 100 evaluable tumor cells)/indeterminate (tumor cell membrane scoring hampered by high cytoplasmic staining or melanin content)

- BRAF status
  - BRAF V600 mutation positive vs
  - BRAF V600 wild type
- AJCC M stage at screening (See [Appendix 7](#))
  - M0/M1any(0) vs
  - M1any(1)

Note: participants whose PD-L1 status is indeterminate/not evaluable will be classified with participant where PD-L1 expression is < 1%.

The randomization procedures will be carried out via permuted blocks within each stratum, defined by combination of PD-L1 status (positive,  $\geq 1\%$ , negative/indeterminate), BRAF V600 mutational status (BRAF mutation positive, BRAF wild type), and M Stage (M0/M1any[0], M1any[1]). The exact procedures for using the IRT will be detailed in the IRT manual.

### **7.3 Blinding**

**Per Revised Protocol 01, the study will be unblinded (see [Section 3.1.1](#)).**

### **7.4 Dosage Modification**

#### **7.4.1 Nivolumab Dose Modifications**

No dose modifications for nivolumab are permitted.

#### **7.4.2 BMS-986205 Dose Modifications**

A dose reduction of BMS-986205 is defined as a change from a 100 mg QD tablet to a 50 mg QD tablet.

Doses of BMS-986205 should be reduced for the following AEs attributable to study therapy that do not otherwise meet criteria for discontinuation:

- Grade 3 fatigue, nausea, vomiting, or anemia related to study treatment
- Methemoglobin  $\geq 15\%$
- Clinically significant elevations in methemoglobin (generally 10%, with a normal hemoglobin level) with any associated Grade 3 AE (hypoxia, dyspnea, confusion, etc.) attributable to sustained elevations of methemoglobin and not attributable to another etiology
- QTcF > 500 msec confirmed by at least 1 repeat ECG and at least 60 msec above baseline (See [Appendix 9](#))

Dose modification and interruption of BMS-986205 may occur in the setting of lower grade AEs and/or be more conservative than indicated above based on the clinical judgment of the investigator and in consultation with the BMS Medical Monitor/designee. For an AE requiring dose modification, BMS-986205 should be delayed to allow improvement of the AE, even if the AE does not otherwise meet criteria for dose delay ([Section 7.4.3](#)).

Re-escalation of BMS-986205 will not be permitted once the dose of BMS-986205 has been reduced for a participant.

Only one dose reduction is permitted. The participant must discontinue study treatments if a subsequent dose reduction of BMS-986205 is required (see [Section 8.1.1](#)).

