#### **7.4.3 Dose Delay (BMS-986205 and Nivolumab)**

BMS-986205 and nivolumab administration should be delayed for the following:

- Grade 2 non-skin, drug-related AE, with the exception of fatigue, nausea, vomiting and anemia
- Grade 2 drug-related creatinine, AST, ALT and/or Total Bilirubin abnormalities
- Grade 3 skin, drug-related AE
- Grade 3 drug-related fatigue, nausea, vomiting, and anemia
- Grade 3 drug-related laboratory abnormality, with the following exceptions:
  - Grade 3 lymphopenia or asymptomatic amylase or lipase elevations do not require dose delay
  - Grade  $\geq 3$  AST, ALT, Total Bilirubin will require dose discontinuation (see [Section 8.1.1](#))
- Any AE, laboratory abnormality, or intercurrent illness which, in the judgment of the investigator, warrants delaying the dose of study medication

In addition, **only BMS-986205** should be delayed for the following:

- Methemoglobin  $\geq 15\%$
- Clinically significant elevations in methemoglobin (generally 10% with a normal hemoglobin level) with any associated Grade 3 AE (hypoxia, dyspnea, confusion, etc.) attributable to sustained elevations of methemoglobin and not attributable to another etiology
- QTcF  $> 500$  msec confirmed by at least 1 repeat ECG and at least 60 msec above baseline (See [Appendix 9](#))

[Appendix 14](#) presents the above criteria in tabular format.

If nivolumab dosing is delayed for reasons other than study drug toxicity (eg, administrative issues, holidays, etc), BMS-986205 dosing should continue uninterrupted.

Participants may continue to receive nivolumab during dose delays of BMS-986205 for elevations of methemoglobin and associated events, as well as QTcF prolongations.

For participants with methemoglobin elevations with associated Grade 3 AEs, if contribution of nivolumab to the associated AE cannot be ruled out (eg, a participant with dyspnea in whom pneumonitis has not yet been ruled out), nivolumab dosing should be delayed as well. See [Section 7.7.4](#) for management of methemoglobinemia.

If BMS-986205 dosing is delayed, dose reduction may be necessary. See [Section 7.4.2](#).

If dosing is resumed after a delay, BMS-986205 may be resumed as soon as the criteria to resume treatment are met (see [Section 7.4.4](#)). Nivolumab should be resumed as soon as possible after criteria to resume treatment are met, but may be resumed later than BMS-986205 given the differences in each drug's administration.

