All participants who discontinue study treatment should comply with protocol specified follow-up procedures as outlined in [Section 2](#). The only exception to this requirement is when a participant withdraws consent for all study procedures including post-treatment study follow-up or loses the ability to consent freely (ie, is imprisoned or involuntarily incarcerated for the treatment of either a psychiatric or physical illness).

The assessment for discontinuation of nivolumab should be made separately from the assessment made for discontinuation of BMS-986205. Although there is overlap among the discontinuation criteria, if discontinuation criteria are met for BMS-986205 but not for nivolumab, treatment with nivolumab may continue if BMS-986205 is discontinued. If a participant discontinues nivolumab, they must also discontinue BMS-986205.

If a participant receiving nivolumab/BMS-986205 combination meets criteria for discontinuation and investigator is unable to determine whether the event is related to both or one study drug, the participant should discontinue both nivolumab and BMS-986205 and be taken off the treatment phase of the study.

If study treatment is discontinued prior to the participant's completion of the study, the reason for the discontinuation must be documented in the participant's medical records and entered on the appropriate eCRF page.

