### **8.1.1 BMS-986205 and Nivolumab Dose Discontinuation**

BMS-986205 and nivolumab treatment should be permanently discontinued for the following:

- Any occurrence of serotonin syndrome
- Any Grade 2 drug-related uveitis, eye pain or blurred vision that does not respond to topical therapy and does not improve to Grade 1 severity within the time frame permitted for dose delays OR requires systemic treatment
- Any event requiring more than 1 dose reduction of BMS-986205 (see [Section 7.4.2](#)), except for those related to methemoglobinemia or QTc prolongations, which require only discontinuation of BMS-986205 alone; subjects may continue to receive nivolumab in these situations (see also [Section 8.1.2](#))
- Any drug-related event requiring 10 mg per day or greater prednisone or equivalent for more than 12 weeks, except for adrenal replacement steroid dose >10mg.
- Immune-mediated encephalitis of any grade
- Any Grade 3 non-skin, drug-related AE lasting > 7 days, or recurs with the following exceptions for laboratory abnormalities, diarrhea, colitis, neurologic toxicity, drug-related uveitis, pneumonitis, bronchospasm, hypersensitivity reactions, infusion reactions, and endocrinopathies:
  - Grade 3 drug-related diarrhea, colitis, neurologic toxicity, uveitis, pneumonitis, bronchospasm, myocarditis, hypersensitivity reaction, or infusion reaction of any duration requires discontinuation
  - Grade 3 drug-related endocrinopathies, adequately controlled with only physiologic hormone replacement do not require discontinuation. Adrenal insufficiency requires discontinuation regardless of control with hormone replacement.
  - Grade 3 drug-related laboratory abnormalities do not require treatment discontinuation except:
    - ◆ Grade 3 drug-related thrombocytopenia > 7 days or associated with bleeding requires discontinuation
    - ◆ Any drug-related liver function test (LFT) abnormality that meets the following criteria require discontinuation:
      - Grade  $\geq 3$  drug-related AST, ALT or Total Bilirubin requires discontinuation\*
      - Concurrent AST or ALT > 3 x ULN and total bilirubin > 2x ULN
- \* In most cases of Grade 3 AST or ALT elevation, study treatment(s) will be permanently discontinued. If the investigator determines a possible favorable benefit/risk ratio that warrants continuation of study treatment(s), a discussion between the investigator and the BMS Medical Monitor/designee must occur.

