### **8.1.2 BMS-986205 Dose Discontinuation**

The following events require discontinuation of BMS-986205 only; nivolumab may continue to be administered unless other events occur that would require delay or discontinuation of nivolumab as described in [Sections 7.4.3](#) and [8.1.1](#).

- Any event requiring more than 1 dose reduction of BMS-986205
- Any AE, laboratory abnormality, or intercurrent illness which, in the judgment of the investigator, presents a substantial clinical risk to the participant with continued BMS-986205 dosing
- For participants who delay BMS-986205 but continue nivolumab (see [Section 7.4.3](#)), any dose delay of BMS-986205 lasting > 10 weeks will result in the discontinuation of both BMS-986205 only.
- Per Revised Protocol 01, participants are permitted to discontinue BMS-986205, and continue nivolumab at investigator discretion (see [Section 3.1.1](#))
- Any occurrence of serotonin syndrome

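### Protocol 7.4.2 stops study treatments at a second BMS-986205 reduction without the methemoglobinemia/QTc exception in the 8.1.1 rule it cites

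*Protocol*

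**What the plan says.** Protocol Section 7.4.2 defines a single permitted reduction of BMS-986205, from 100 mg to 50 mg daily. Its triggers are Grade 3 fatigue, nausea, vomiting or anemia; methemoglobin of 15% or more; a clinically significant methemoglobin elevation with an associated Grade 3 event; and confirmed QTcF prolongation. It closes with "The participant must discontinue study treatments if a subsequent dose reduction of BMS-986205 is required" and a pointer to Section 8.1.1. Section 7 defines study treatment broadly, and Table 7-1 lists both nivolumab and BMS-986205.

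Section 8.1.1 lists events that stop both drugs. One is any event needing more than one BMS-986205 reduction, "except for those related to methemoglobinemia or QTc prolongations, which require only discontinuation of BMS-986205 alone". That bullet adds that nivolumab may continue in these situations and refers on to Section 8.1.2.

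Section 8.1 has the two drugs assessed separately: "if discontinuation criteria are met for BMS-986205 but not for nivolumab, treatment with nivolumab may continue if BMS-986205 is discontinued". Where the investigator cannot tell which drug caused the event, "the participant should discontinue both nivolumab and BMS-986205 and be taken off the treatment phase of the study".

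Section 8.1.2 opens "The following events require discontinuation of BMS-986205 only; nivolumab may continue to be administered", subject to other events that call for nivolumab delay or discontinuation. Its first bullet is "Any event requiring more than 1 dose reduction of BMS-986205", with no limit by type of event.

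Section 7.4.3 says of delays: "Participants may continue to receive nivolumab during dose delays of BMS-986205 for elevations of methemoglobin and associated events", and likewise for QTcF prolongation. Nivolumab is delayed too, for methemoglobin elevations with associated Grade 3 events, "if contribution of nivolumab to the associated AE cannot be ruled out".

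**The concern.** The 7.4.2 sentence is a mandatory, permanent stopping rule. For methemoglobin and QTcF events it cannot be followed literally together with the 8.1.1 bullet that it cites. A site that acts on 7.4.2 alone would end nivolumab for a participant whom the protocol allows to stay on it, and nivolumab is the treatment that Arm A may continue as monotherapy under Revised Protocol 01.

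The 8.1.2 bullet errs in the other direction. Read alone, it could keep nivolumab going after a second-reduction event for which 8.1.1 stops both drugs. Section 9 allows no waivers or exemptions, so sites should not have to choose between these texts.

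**Working it through.** No figure in the plan bears on this point and no arithmetic applies. The check sets the rules side by side for a participant already at 50 mg who would need a further reduction. Each cell shows what stops when that text is read on its own.

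| Event behind the second reduction | 7.4.2, closing sentence | 8.1.1, second-reduction bullet | 8.1.2, first bullet |
|---|---|---|---|
| Methemoglobin elevation or QTcF prolongation | Both drugs | BMS-986205 only | BMS-986205 only |
| Grade 3 fatigue, nausea, vomiting or anemia | Both drugs | Both drugs | BMS-986205 only |

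**First row.** Section 7.4.2 stands alone against 8.1.1 and 8.1.2. Section 7.4.3 withholds only BMS-986205 for these same triggers, and 8.1 lets nivolumab continue when only the BMS-986205 criteria are met. The sentence in 7.4.2 is therefore the one out of line.

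**Second row.** Section 8.1.2 is the odd one out. Its opening does not clearly repair this. It yields to *other* events that require nivolumab to be delayed or stopped, whereas here the same event is listed in both sections. The 8.1.1 exception refers the reader to 8.1.2, which suggests that the 8.1.2 bullet was meant to receive only the excepted events.

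**How far the second row reaches.** A separate 8.1.1 bullet stops both drugs for a Grade 3 non-skin drug-related event that lasts more than 7 days or recurs. A recurrence of the same Grade 3 fatigue, nausea or vomiting, or a prolonged episode, is caught there whatever 8.1.2 says. What remains is:
- a second reduction for a different, short-lived Grade 3 event;
- anemia, if it is handled as a laboratory abnormality;
- a reduction for a lower-grade event, which 7.4.2 allows on clinical judgment.

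**The same bullet and the first row.** It may also catch some Grade 3 events associated with methemoglobin. It does not clearly cover methemoglobin of 15% or more alone, or QTcF prolongation. If it overrode the exception for all these events, the exception would have no use. The first-row conflict therefore remains.

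**Who can be affected.** Only Arm A participants who stayed on BMS-986205 after Revised Protocol 01, are already at 50 mg, and then meet a further trigger. The documents give no count.

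**The case against.** The strongest reply is that 7.4.2 is shorthand for the rule it points to. The sentence names 8.1.1; the 8.1.1 bullet cites 7.4.2 in return and gives the exception in full. Section 8.1 separately requires drug-by-drug assessment. Investigators may also drop BMS-986205 at their discretion and keep nivolumab, which suits exactly this participant. No estimate or test depends on the rule, since the study is closed to enrollment, unblinded and limited to safety. All of this stands, and it is why the impact is small. It does not make the 7.4.2 sentence correct, because a mandatory instruction should carry its own exception.

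On 8.1.2, the objection is that the sponsor may have meant the broad bullet. It fits separate assessment of the drugs, and the Revised Protocol 01 change history lists both 8.1.1 and 8.1.2 as updated, so that history does not settle the matter. Against this, 7.4.2 and 8.1.1 both stop both drugs for the Grade 3 events, and the exception in 8.1.1 leads into 8.1.2. The text favors 8.1.1, but the sponsor should confirm it.

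A reader might infer a larger problem by counting the triggers on which the sections differ, or by working out the weeks of nivolumab that could be lost. The documents do not support either as a measure of size. Trigger counts compare single bullets and ignore the separate 8.1.1 bullet on prolonged or recurrent Grade 3 events. A weeks-lost figure would need a very late randomization, a second trigger soon after the current revision, no progression through week 104, and a site that ignores the printed reference.

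**Conclusion.** This is an internal inconsistency: wrong as written, minor, and worth correcting. For methemoglobinemia and QTc events the 7.4.2 sentence contradicts the rule it cites, and the rest of the visible protocol sides with 8.1.1. The unrestricted first bullet of 8.1.2 is a linked and narrower fault, which matters mainly where the 8.1.1 bullet on prolonged or recurrent Grade 3 events does not already apply.

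The number of participants exposed is not stated and could be zero. A reader might infer that nivolumab has been stopped wrongly, or that the protocol gives no usable answer. Neither follows: the documents report no such case, and the cross-reference leads to the right rule.

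The conclusion assumes that study treatments in 7.4.2 carries the Section 7 and Table 7-1 meaning. Section 7.7.4 and Appendix 14 are not visible and may restate the rule, but they could not make the 7.4.2 and 8.1.1 sentences agree.

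**What to change.** In Section 7.4.2, replace the closing sentence with:

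> If a subsequent dose reduction of BMS-986205 is required, discontinue study treatments (see Section 8.1.1), except for methemoglobinemia or QTc prolongation, where only BMS-986205 is discontinued and nivolumab may continue unless other criteria in Sections 7.4.3, 8.1 or 8.1.1 require its delay or discontinuation.

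The closing condition preserves the rule to stop both drugs when attribution is unclear, the nivolumab delay rule in 7.4.3, and the remaining 8.1.1 criteria.

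In Section 8.1.2, ask the sponsor to confirm that 8.1.1 states the intent for other events. If so, limit the first bullet to methemoglobinemia or QTc events that need more than one reduction, and point to 8.1.1 for all others.

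The cost is one sentence and one bullet, with no new data or procedures. The 7.4.2 change could go in an administrative letter, a route the sponsor has already used for clarifications, or in the next revision. The 8.1.2 change would require nivolumab to stop in cases where that bullet, read alone, lets it continue, so the sponsor should decide whether a letter is enough.

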#### **7.4.3 Dose Delay (BMS-986205 and Nivolumab)**

BMS-986205 and nivolumab administration should be delayed for the following:

- Grade 2 non-skin, drug-related AE, with the exception of fatigue, nausea, vomiting and anemia
- Grade 2 drug-related creatinine, AST, ALT and/or Total Bilirubin abnormalities
- Grade 3 skin, drug-related AE
- Grade 3 drug-related fatigue, nausea, vomiting, and anemia
- Grade 3 drug-related laboratory abnormality, with the following exceptions:
  - Grade 3 lymphopenia or asymptomatic amylase or lipase elevations do not require dose delay
  - Grade  $\geq 3$  AST, ALT, Total Bilirubin will require dose discontinuation (see [Section 8.1.1](#))
- Any AE, laboratory abnormality, or intercurrent illness which, in the judgment of the investigator, warrants delaying the dose of study medication

In addition, **only BMS-986205** should be delayed for the following:

- Methemoglobin  $\geq 15\%$
- Clinically significant elevations in methemoglobin (generally 10% with a normal hemoglobin level) with any associated Grade 3 AE (hypoxia, dyspnea, confusion, etc.) attributable to sustained elevations of methemoglobin and not attributable to another etiology
- QTcF  $> 500$  msec confirmed by at least 1 repeat ECG and at least 60 msec above baseline (See [Appendix 9](#))

[Appendix 14](#) presents the above criteria in tabular format.

If nivolumab dosing is delayed for reasons other than study drug toxicity (eg, administrative issues, holidays, etc), BMS-986205 dosing should continue uninterrupted.

Participants may continue to receive nivolumab during dose delays of BMS-986205 for elevations of methemoglobin and associated events, as well as QTcF prolongations.

For participants with methemoglobin elevations with associated Grade 3 AEs, if contribution of nivolumab to the associated AE cannot be ruled out (eg, a participant with dyspnea in whom pneumonitis has not yet been ruled out), nivolumab dosing should be delayed as well. See [Section 7.7.4](#) for management of methemoglobinemia.

If BMS-986205 dosing is delayed, dose reduction may be necessary. See [Section 7.4.2](#).

If dosing is resumed after a delay, BMS-986205 may be resumed as soon as the criteria to resume treatment are met (see [Section 7.4.4](#)). Nivolumab should be resumed as soon as possible after criteria to resume treatment are met, but may be resumed later than BMS-986205 given the differences in each drug's administration.

Participants who require delay of any study treatment should be re-evaluated weekly or more frequently if clinically indicated and resume dosing when re-treatment criteria are met.

